information. Qualifying providers will be recruited for the study and will be formally consented. The enrolled providers will be randomized to treatment and control groups (using the OneSheet vs. NOT using the OneSheet). The participating providers that have been randomized to the treatment group will be given instructions on how to access and use the OneSheet when treating patients' chronic pain. These providers will also be given ongoing technical support and assistance with integrating the OneSheet into their clinical workflows. Those participating providers who have been randomized to the control group will not be given any information or instructions on accessing and using the OneSheet. At Eskenazi, when a qualifying patient, identified by Regenstrief through an algorithm developed in collaboration with the researchers, comes to a visit with a participating provider in the treatment group, a BPA will appear in the patient's record, alerting the provider to consider utilizing the OneSheet for that patient's chronic pain management during the visit. Eskenazi will share the MRNs of qualifying patients, and dates of qualifying visits with Regenstrief Data Core, who will collect outcome measure data, remove patient identifiers (with the exception of dates), and share this limited data set with the research team for analysis. At Wake Forest, when a qualifying patient, identified through the same process, comes to a visit with a participating provider in the treatment group, a BPA will appear in the patient's record, alerting the provider to consider utilizing the OneSheet for the patient's chronic pain management during the visit. Wake Forest Baptist Health will share the MRNs of qualifying patients, and dates of qualifying visits with an honest broker, who will collect outcome measure data, remove patient identifiers (with the exception of dates), and share this limited data set with the research team for analysis. At both sites, formal informed consent and HIPAA authorization will not be obtained from qualifying patients being treated by participating providers.

q23358

Will any non-English study documents be uploaded?

No

q24919

Is this research funded by, or has a funding application been submitted to, a federal agency? This includes federal pass- through funding.

Yes

q23234

List inclusion criteria - eligibility criteria for subjects.

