Describe how potential subjects will be initially identified. Potential subjects will be initially identified through the listing of primary care providers at each of Eskenazi's or Wake Forest's primary care clinics on their website. Other providers will be identified by having previously collaborated on prior projects with the research team. Additionally, at both sites, researchers will identify potential subjects at presentations at clinic meetings, after receiving approval from the clinic's management. Eligible clinic visits at Eskenazi Health clinics will be identified by Regenstrief Institute Data Core and Eskenazi Health. The researchers will provide criteria for eligibility, and Regenstrief and Eskenazi will work together to identify them. Eligible clinic visits at Wake Forest Baptist Health clinics will be identified by Wake Forest Baptist Health working with an honest broker similar to the Regenstrief Institute Data Core. The researchers will provide criteria for eligibility, and the health system (WFBH) and the honest broker will work together to identify them. The researchers will not be privy to the list of eligible patients or clinic visits at either trial site.

q30002

Check any of the following sources of information which will be used to identify potential subjects.

Subject self-referral in response to recruitment materials

q30003

Describe how potential subjects will be initially contacted. Researchers will visit primary care clinics and present the research project to all primary care providers there through a powerpoint presentation and handouts/fliers. Interested eligible providers identified at the clinic presentations will be followed up with by e-mail by research staff. Providers who have previously collaborated with the research team will also be contacted by e-mail, and asked to refer other providers in their clinic who may be interested in participating. Because of operations changes related to covid-19, if visiting the clinic in person is not acceptable, researchers may also work with the primary care clinics to present the powerpoint presentation through a teleconference or a virtual meeting with a software like Zoom. The powerpoint and handouts will be shared through email.

q23237

Check any of the following recruitment materials which will be used to contact potential subjects.

Direct
Mail/Email
Flyers/Brochures Verbal Scripts

q25426b

Select any of the following circumstances which apply to this research.

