**Nudging Primary Care Providers toward Guideline-Recommended
Opioid Prescribing through Easier and More Convenient EHR
Information Design**

R33 Clinical Trial
MPIs: [name] and [name]

NCT04295135

IRB #1911922583

Mar 5, 2024

CT. Gov: Statistical Analysis Plan

Study title: Nudging Primary Care Providers toward Guideline-Recommended Opioid Prescribing through Easier and More Convenient EHR Information Design

To assess the OneSheet effects on guideline-concordant care, we collected data from participating clinicians' visits with patients meeting several criteria described below. The criteria were: 1) 18+ years old; 2) no cancer diagnosis in the prior 3 years; 3) meet the following indications of chronic pain over the most recent 24 months:

- a. 3+ unique* instances of a qualifying pain diagnosis (either billed diagnosis or problem list) OR
- b. 3+ unique* prescriptions for one or more of the following drugs: an opioid ("opioid agonist," "opioid partial agonist," "opioid combinations"), Tramadol, Nortriptyline, Amitriptyline, Gabapentin, Pregabalin, Duloxetine, desipramine, milnacipran, tapentadol OR
- c. 2 unique* instances of a qualifying pain diagnosis AND 2+ unique* pain medication prescriptions containing one or more of the drugs listed in b.

*"unique", for Diagnoses and medications was defined as separated by at least 30 days from any previous qualifying diagnosis or prescription.

Because chronic pain treatment is often discussed during visits not explicitly identified as related to chronic pain, any visit that a qualifying patient has with a participating primary care clinician was considered as a qualifying visit for the trial. The data for qualifying visits was collected one year before OneSheet access was granted (October/November 2019) to May 2022 (18 months of the trial period).

Outcomes: We constructed six visit-level binary outcomes that could be measured with electronic health record (EHR) data and reflected recommendations in the 2016 CDC opioid prescribing guideline: 1) recording pain-related goals in the last 90 days; 2) recording pain and function via the Pain, Enjoyment, and General (PEG) assessment in the last 90 days; 3) checking the prescription drug monitoring program (PDMP) in the last 90 days; 4) assessing UDS results in the last calendar year; 5) ordering medications for opioid use disorder (MOUD) within seven days of the visit; and 6) ordering Naloxone within seven days of the visit.

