Each outcome was set to 1 if the patient met the lookback criteria outlined above (e.g., 90 days for pain-related goals, PEG, and PDMP; 1 year for UDS, seven days for MOUD and Naloxone), or if the provider completed a given task one week following the visit (a 7-day grace period). For PDMP review, there was no one-week grace period because PDMP review is recommended by the CDC (and mandated by many states) to occur at the time of opioid prescribing.

The outcomes of pain-related pain and function goals and PEG assessments were evaluated for all patients with chronic pain, while the CDC recommendations for PDMP checking, UDS review, MOUD ordering, and Naloxone ordering only apply to patients on long-term opioid therapy (LTOT). We identified visits for patients on LTOT as those involving an opioid analgesic prescription lasting at least 28 days, per the Agency for Healthcare Research and Quality's CDS Connect recommendation for assessing opioid therapy (Agency for Healthcare Research and Quality, 2018).

As an example outcome, if a patient on LTOT had not had a UDS result in the last calendar year, but the provider ordered a UDS on the day of the visit, the outcome would be set to 1 (guideline-concordant). Similarly, if the patient had a UDS result in the last calendar year, the outcome would be set to 1 because at the time of the visit, the clinician was concordant with the CDC guideline recommendations for UDS review. If both a) a UDS had not been completed in the last year and b) the clinician did not order a UDS within one week of the visit, the outcome would be set to 0 (non-concordant).

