Statistical Analysis: We used descriptive statistics to compare the demographic characteristics of clinicians assigned to the intervention group versus the control. We computed our outcomes at the patient-visit level for visits by qualifying patients with study providers for the 12 months before the OneSheet went live (the baseline period) and 18 months following OneSheet go-live. We excluded patients from the sample who had visits during the study period with both treatment and control clinicians to ensure that outcomes were not compared across trial arms for the same patient. To estimate the effect of OneSheet on our outcomes, we used a multi-level linear probability model including patient demographics, clinician random effects, and indicator variables for a) site; b) treatment and control clinicians; and c) pre-/post-OneSheet go-live. We included an interaction term for treatment and post-OneSheet go-live, the coefficient for which estimates the causal effect of OneSheet on our outcomes of interest. Statistical tests were 2-tailed, and p-values < 0.05 were considered statistically significant. Data analyses were performed from November 2022 to September 2023 using *tidyverse*, *lubridate*, *fixest*, and *lme4* R packages in RStudio (Bates et al., 2015; Berge, 2018; Grolemund et al., 2011; Wickman, 2017).

References:

Agency for Healthcare Research and Quality, 2018. Recommendation 7: Opioid therapy risk assessment. Retrieved March 1, 2024, from
<https://cds.ahrq.gov/cdsconnect/artifact/recommendation-7-opioid-therapy-risk-assessment>

Wickham H. The tidyverse. R package ver 1 1 1 [Internet]. 2017; Available from:
https://slides.nyhackr.org/presentations/The-Tidyverse_Hadley-Wickham.pdf

<https://www.jstatsoft.org/v40/i03/>

Bergé L (2018). “Efficient estimation of maximum likelihood models with multiple fixed-effects: the R package FENmlm.” CREA Discussion Papers.

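### The model has no site-by-period term, so a difference between the two health systems in background change would shift the OneSheet estimate in proportion to any arm imbalance in site mix

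*SAP*

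**What the plan says.** The SAP's Statistical Analysis section states that "we used a multi-level linear probability model including patient demographics, clinician random effects". Three further main effects complete the fixed part of the model: "indicator variables for a) site; b) treatment and control clinicians; and c) pre-/post-OneSheet go-live". The only interaction is the one that carries the result: "We included an interaction term for treatment and post-OneSheet go-live, the coefficient for which estimates the causal effect of OneSheet". The section lists no site-by-post term, no site-specific calendar effect, no random period slope and no estimate by site. Each test is judged on its own: "Statistical tests were 2-tailed, and p-values < 0.05 were considered statistically significant".

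The data cover 12 months before and 18 months after go-live, "collected one year before OneSheet access was granted (October/November 2019) to May 2022", at the Eskenazi and Wake Forest Baptist Health primary care clinics. On allocation, the Protocol (section B, q22123) says "The enrolled providers will be randomized to treatment and control groups", and the IRB Amendments table records that this was done by individual clinician. Neither document says whether allocation was stratified by site, or how clinicians or visits divide between sites and arms.

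**The concern.** A treatment-by-post coefficient takes the controls' change over time as what would have happened to the treatment clinicians. Here that change is a single number pooled over two organisations for 30 months. If usual care moved differently at the two systems, and one arm has relatively more of its visits at the system that moved more, part of that movement is credited to OneSheet or subtracted from it. The reported standard error does not allow for this, because a clinician random intercept absorbs differences in level and not site-specific differences in change.

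Several features of the design make an exactly equal site mix unlikely:

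- No stratification by site is stated.
- Outcomes are analysed per visit, so busy clinicians weigh more. Equal clinician headcounts would not balance visits.
- The IRB Amendments table records provider turnover and a second recruitment.
- Patients seen by clinicians of both arms are dropped.
- Four of the six outcomes use only visits of patients on long-term opioid therapy, where the mix may differ again.

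**Working it through.** The documents give no power calculation, outcome rates, clinician variance or site split, so there is no stated figure to reproduce. The check is an algebraic result followed by simulations under stated assumptions.

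**1. The shift.** Let D be the difference between sites in background pre/post change. Let g be the treatment-arm share minus the control-arm share of visits at one site, with clinicians weighted as the model weights them. With no true effect and no site × post term:

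shift in the treatment × post coefficient = D × g

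Example: background change is +10 points at site A and 0 at site B. Visits at A make up 57.5% of the treatment arm and 42.5% of the control arm (g = 15 points). The treatment arm changes by 0.575 × 10 = 5.75 points and the control arm by 0.425 × 10 = 4.25. The difference is 1.5 points, although OneSheet did nothing.

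Fitting the model by generalised least squares, noise-free, gave the same rule:

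| D (points) | g = 0 | g = 5 | g = 10 | g = 20 |
|---|---|---|---|---|
| 5 | 0 | 0.25 | 0.5 | 1.0 |
| 10 | 0 | 0.5 | 1.0 | 2.0 |
| 20 | 0 | 1.0 | 2.0 | 4.0 |

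With site × post added, the shift was 0.0 in every cell, given an effect common to both sites.

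**2. How large g is by chance.** Assume 1:1 unstratified allocation and sites split 50:50. The SD of the gap in clinician share is √(0.25 × 4/(n − 1)). This is 6.3 points for n = 250 (the enrolment figure in Protocol q711a) and 11.3 points for n = 80 (an assumed smaller analysed number). With D = 10 points, the SD of the shift is 0.63 or 1.13 points. As a check, the simulated SD of the estimate with equal visit counts at D = 0 is 0.81 (n = 250) and 1.49 (n = 80). Combining, √(0.81² + 0.63²) = 1.03 and √(1.49² + 1.13²) = 1.87. The simulated values at D = 10 were 1.04 and 1.87. Mean bias over allocations was within 0.1 point of zero throughout.

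**3. Information lost.** Assume 150 clinicians, half per site, exponential visit counts with mean 120, and a 30% baseline rate. Unstratified, with no variation between clinicians in change and independent visits, the SDs in percentage points are:

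| D (points) | Without site × post | With site × post | Loss = 1 − (with/without)² |
|---|---|---|---|
| 0 | 1.38 | 1.38 | 0 |
| 5 | 1.52 | 1.41 | 14% |
| 10 | 1.80 | 1.40 | 40% |
| 15 | 2.23 | 1.40 | 61% |

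These are upper-end figures, because the setting leaves out other sources of variance. At D = 10 points, approximate losses when those are added (simulated, so accurate to a few percentage points) are:

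| Added variance | Unstratified | Stratified by site |
|---|---|---|
| None | 40% | 25% |
| Clinician change with SD 10 points | 14% | 9% |
| Visit design effect of 3 | 19% | 9% |
| Both | 9% | 4 to 5% |

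At D = 5 points with both additions the loss is 1 to 3%.

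**4. Type I error.** Assume n = 250, D = 10 points, visit variance 0.20, clinician variance 0.02, and no clinician variation in change (again the upper end). The nominal 5% test rejects in:

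- 11.3% of trials with simple randomisation and equal visits;
- 21.5% with simple randomisation and unequal visits;
- 14.7% with stratification and unequal visits;
- 4.7% with stratification and equal visits.

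With site × post added, the range over all settings tried was 3.9% to 6.4%, close to nominal.

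**The case against.** The strongest reply is that a difference-in-differences among individually randomised clinicians, with a site main effect, is a defensible specification. The error has no expected direction, and nothing in the documents shows that D or g differs from zero. All of that stands.

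A reader might infer more from four places, and the documents do not support it.

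- **State rules.** The SAP says "PDMP review is recommended by the CDC (and mandated by many states". It names no state and no rule change during the study. A standing difference in mandates is a difference in level, which the site indicator absorbs, and it concerns one outcome of six.
- **Covid-19.** The Protocol's phrase "Because of operations changes related to covid-19" (q30003) explains why recruitment presentations might move online. It says nothing about differing effects on care at the two sites. A shock common to both is absorbed by the post indicator.
- **Go-live.** The month range in the SAP does not say that go-live months differed by site, or that the post indicator was not already site-specific.
- **Second recruitment.** It was at both sites, so it may alter the mix but does not imply that it did so unequally.

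It would also be wrong to say that controls at one system simply replace those at the other. Each site is expected to have its own controls, and the model pools them. Pure cross-site substitution would need arm and site to coincide, which individual randomisation makes implausible.

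What the reply does not remove is that a zero average over hypothetical allocations does not protect the one allocation that occurred. The assumption of equal background change is also unnecessary when one term would relax it.

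**Conclusion.** The point holds in conditional form. The model assumes equal background change at two health systems, and any departure moves the effect estimate by D × g in the realised trial. That is 1.5 points for an assumed 10-point difference in change and 15-point gap in site share, and nothing if either is zero. Actual bias cannot be shown from the documents.

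At D = 10 points the loss of information runs from about 4% (stratified by site, clinicians varying in change, visits clustered) to about 40% (unstratified, neither); at D = 0 it is about nil. The 40% figure should not be quoted alone, since it needs every unfavourable assumption together. The range rests on an assumed 150 clinicians, an even site split and a 30% baseline rate. This is a near-free improvement to the analysis and not a demonstrated error in the result.

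**What to change.** Add a site × post-go-live interaction to the model in the SAP's Statistical Analysis section, so that treatment clinicians are compared with concurrent controls at their own site. If the OneSheet effect itself differs by site, the coefficient is then a weighted average of the site effects, and the report should say so.

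Report visits by arm, site and period for each outcome's analysis set, including the visits on long-term opioid therapy, so that readers can see g. State whether allocation was stratified by site.

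The SAP dates the analyses November 2022 to September 2023. The refit should therefore be labelled as added afterwards and shown beside the original estimates, whichever way they move.

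The cost is one degree of freedom, one re-run and a small table. Site and visit date are already collected, and the simulations showed no visible loss of precision when the sites changed alike (SD 0.81 points with and without the term at n = 250).

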9/16/20	Individual randomization instead of clinic level, updated ICF total number of participants - a005
8/6/21	Adding second recruitment at both sites to increase sample size due to provider turnover-v5

Administrative Details Form

Protocol Details

9031

Protocol Type

Expedited

Billing Account #

Study Status

Submission Details

9000

Submission Review Level

Expedited

9030

Expedited Category.

Category 5: Data or specimens that have been or will be collected for nonresearch purposes

Category 7: Survey, interview, focus groups, human factor, group behavior or characteristics

9002

Criteria for Approval. Select to confirm.

Approved: The criteria for approval of the research are satisfied in accordance with IU HRPP Policies, and applicable federal regulations.

Protocol Determinations

9003

Protocol Level of Risk.

Minimal risk

9020

Is renewal required for this research?

No

9004

Check all determinations that need to be made.

Informed Consent Waiver

HIPAA Waiver

Certificate of Confidentiality

9005

Informed Consent Waivers

Waiver of informed consent granted in accordance with IU HRPP Policies

9006

HIPAA Waivers

Participation

9010

Brief description of PHI - Participation

Patient demographics Healthcare encounter location, type, provider, and date

Chronic pain diagnosis and date Patient goal type and date Pain and function

assessment (PEG) results and date of assessment PDMP check completion

date Laboratory, procedure, medication, and referral orders Opioid risk tool

results and date of assessment Patient MRN

9009

Participation HIPAA Waiver

Waiver of authorization criteria satisfied in accordance with 45 CFR 164.512(i) (2)(ii). Waiver of authorization approved in accordance with 45 CFR 164.512(i).

9025

Certificate of Confidentiality.

The research is subject to the NIH Policy for Issuing Certificates of Confidentiality and therefore has been issued a Certificate.

9028

Other Determinations.

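### A single pre/post step is the only control for calendar time over about 30 months: it costs a little precision, and it biases the estimate only if the arms' visits fall in different months

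*SAP*

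**What the plan says.** The SAP's Statistical Analysis section specifies a linear probability model with demographic covariates and a random effect for each clinician. Its remaining main terms are listed as "indicator variables for a) site; b) treatment and control clinicians; and c) pre-/post-OneSheet go-live". The effect is a single coefficient: "We included an interaction term for treatment and post-OneSheet go-live, the coefficient for which estimates the causal effect of OneSheet". No month, quarter, trend or site-by-time term is described. The R packages listed include one for fixed-effects models, but the text mentions no calendar fixed effects.

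Outcomes are computed "for the 12 months before the OneSheet went live (the baseline period) and 18 months following OneSheet go-live". The SAP's opening section dates this window from October/November 2019 to May 2022.

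The protocol adds four relevant facts:
- Section D, item q30003, contains the phrase "Because of operations changes related to covid-19", in a sentence about how researchers would reach clinicians.
- The IRB Amendments table records a move to individual randomisation (9/16/20).
- The same table later records "Adding second recruitment at both sites to increase sample size due to provider turnover" (8/6/21).
- The HIPAA section (q23656) says service dates are in the limited dataset and are needed to study the effect over time.

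Neither document gives visit counts by month and arm.

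**The concern.** The model fits one background level to the 12 baseline months and one to the 18 later months. The baseline runs through most of 2020, when a constant level is hard to take for granted. Clinicians who leave or join part-way do not contribute visits evenly across months. If the arms' visits are spread differently over the months of a period, part of any calendar swing is counted as an effect of OneSheet. This can happen within one site and with a constant true effect, so it is separate from site-specific trends and from an effect that changes over time. At stake are the precision of every treatment-by-post estimate and, if timing differs by arm, its bias.

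**Working it through.** **1. Window.** 12 + 18 = 30 months. A start in 10/2019 puts go-live at 10/2020 and the end at 4/2022; a start in 11/2019 gives 11/2020 and 5/2022. This agrees with the SAP. The second recruitment (8/6/21) came 9 to 10 months after go-live. The documents give no power calculation to reproduce.

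**2. Leakage formula.** Assume no true effect, a month effect g(m) common to both arms, and s(m) as the share of an arm's visits in month m of its period. Ignoring clinician effects, the interaction coefficient is

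Σ over post months of [s_T(m) − s_C(m)] × g(m), minus the same sum over baseline months.

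If the shares match, this is zero for any swing. Otherwise it is the swing times the difference in shares:
- 10-point swing, 10-point difference: 0.10 × 0.10 = 1.0 point.
- 20-point swing, 10-point difference (for example 55% against 45% of baseline visits in the affected months): 2.0 points.
- 5-point swing, 5-point difference: 0.25 points.

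With month indicators the coefficient is 0.0 in every case.

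**3. Simulations with clinician intercepts and no true effect.** All settings are assumptions. The sign depends on which arm loses more clinicians and on the direction of the swing.

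*Set A:* 100 clinicians, 4 visits a month, clinician SD 10 points, clinician-by-period SD 5 points, 20% hired mid-study. Means (SDs) are in points.

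| Turnover and swing | Step | Month indicators |
|---|---|---|
| 30% in both arms, 25 points | 0.0 (2.33) | 0.0 (2.24) |
| 40% vs 20%, 15 points | −0.33 | −0.02 |
| 40% vs 20%, 25 points | −0.60 | −0.08 |
| As above, late hires also 10% vs 30% | −0.97 | −0.15 |

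*Set B:* 250 clinicians, mean 20 visits a month, 30% base rate, clinician SD 10 points, no clinician-by-period variation, a 10-point dip in 4 baseline months, a 10-point rise in the last 9 months, and leavers going early after go-live.

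| Leaving (treatment vs control) | Step | Month indicators | False positives (step vs month) |
|---|---|---|---|
| None | 0.00 (0.48) | 0.00 (0.48) | 3.9% vs 3.4% |
| 30% vs 30% | 0.00 (0.60) | 0.00 (0.53) | 8.0% vs 5.3% |
| 20% vs 40% | 0.71 (0.57) | 0.02 (0.50) | 29.6% vs 3.8% |

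A further set of runs gave about zero bias with equal turnover (SD 2.23 for the step, 2.18 with month indicators) and 0.2 to 0.3 points with 40% against 20%.

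**4. Hand check of the 0.71.** With clinician intercepts the comparison is largely within clinician, so a clinician with 12 baseline and k post months weighs about 12k/(12 + k). Stayers (k = 18) weigh 7.2. Leavers (k = 2 to 9) average 3.63. Half of a stayer's post months carry the 10-point rise, which is 5 points on average; a leaver's carry none. The stayers' weight share is 0.8 × 7.2 / (0.8 × 7.2 + 0.2 × 3.63) = 0.888 in treatment and 0.6 × 7.2 / (0.6 × 7.2 + 0.4 × 3.63) = 0.748 in control. The bias is (0.888 − 0.748) × 5 = 0.70 points.

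**5. Precision with balanced turnover.** The variance saved is 1 − (2.24/2.33)² = 7.6% in set A and 1 − (2.18/2.23)² = 4.4% in the further runs. Set B gives 1 − (0.53/0.60)² = 22%, because without clinician-by-period variation there is little other noise.

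**6. Bias against the standard error, set A (about 2.3).** 0.33/2.3 = 0.14, 0.60/2.3 = 0.26 and 0.97/2.3 = 0.42. With a calibrated standard error, the two-sided false-positive rate would be about 5.2%, 5.8% and 7.0%.

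**The case against.** A reader might infer that COVID-19 and turnover have biased the OneSheet estimate. The documents do not support that:
- Individual randomisation with both arms observed over the same calendar window makes shared swings cancel in expectation. Every equal-turnover simulation shows this.
- The amendment entry gives no turnover rate, count or arm. The 40% against 20% is an assumption.
- The protocol's COVID-19 remark concerns recruitment contact. It says nothing about PEG, goals, PDMP, UDS, MOUD or naloxone practice. Four of the six outcomes also look back 90 days or a year, which tends to smooth short dips.
- A clinician recruited in 2021 may have practised at the site throughout. Recruitment is not hiring, and late entry of visits is not documented. In a separate simulation where only late joining differed, by up to 20 percentage points, bias was at most about 0.1 points. The 0.97 in set A therefore depends on its combined assumptions.
- The high false-positive rates in set B rest on its visit volume and on clinicians not varying in their own change. They should not be quoted as this trial's error rate.
- The SAP reports analyses finished in September 2023 and is dated March 2024. Silently changing the main specification now would be a fault of its own.

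All of this stands, and it limits the size of the point. It does not remove it. Turnover happens after randomisation, so equal visit timing is not guaranteed. Chance alone also unbalances timing: with 30% leaving in each arm of set B, the arm difference in the late share of post-go-live visits had an SD of 2.0 points with 250 clinicians and 3.1 with 100.

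**Conclusion.** The point holds as a modest one. The step model is a legitimate analysis of a randomised comparison, and shared calendar swings do not bias it when visit timing is balanced. It then loses a few percent of variance if clinicians vary in their own change, and relatively more if they do not. It is biased only if the arms' visits fall in different months within a period, which the documents neither show nor exclude.

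Under assumed swings of 10 to 25 points and 40% against 20% turnover, with or without unequal late entry, the bias is about 0.2 to 1 point, or roughly 0.1 to 0.4 of a standard error of about 2.3. With the smaller standard error of set B (about 0.5), the same bias would weigh more. Swings, turnover, visit volumes and variances are all assumed, so these figures show scale only and say nothing about what happened in the trial.

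**What to change.** Fit each outcome with calendar-month indicators in place of the single post indicator, keeping the treatment indicator and the treatment-by-post interaction as the effect. Site-by-month indicators are preferable, because common month effects leave site-specific swings uncontrolled. Report this next to the stated pre/post model, labelled as a change made after the analysis, and add a table of visits by month and arm. That table shows directly whether timing differed. If it did not and the two estimates agree, the stated result is stronger.

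The cost is about 28 extra nuisance parameters (29 month indicators replacing one), roughly double by site, which is small at visit level. It also needs one SAP sentence and a re-run. Visit dates are already in the dataset, so no new data are needed. Month indicators would not correct any difference in which kinds of clinicians left each arm.
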